7.5. EXAMINATION OF SUBGROUPS

No subgroup analyses will be performed for this study.

8. OUTPUT PRESENTATIONS

[Appendix 1](#) shows conventions for presentation of data in outputs.

The templates provided with this SAP describe the presentations for this study and therefore the format and content of the summary tables, figures, and listings to be provided by IQVIA Biostatistics.

9. DISPOSITION AND WITHDRAWALS

All patients who completed Part A of the study will be accounted for in Part B of the study.

Patient disposition, withdrawals and reasons for exclusion from each analysis set will be presented for all patients, summarized by treatment sequence for the patients who completed Part A and were randomized in Part B. Number of patients treated and discontinued in each treatment period will also be presented. If the patient discontinued/withdrew, he/she will be allocated to the last treatment period attended.

All protocol deviations collected in Part B will be divided into critical, major or minor categories and will be assigned to the actual treatment group. The major and critical protocol deviations (PD) will be summarized by treatment and all PDs will be presented in a listing for the RND analysis set. Protocol deviations affect the integrity of the drug activity data and will be obtained by the clinical research associates (CRAs) and documented in the clinical trial management system (CTMS).

Document: Z:\RPL554\AZA40375\Biostatistics\Documentation\SAP\Verona RPL554-DP-201 SAP v2.0 – Part B

Author: [name] / [name]

Version Number: 2.0

Version Date: [08JUL2019]

Template No.: CS_TP_BS016 Revision 5

Reference: CS_WI_BS005

Effective Date: 01Apr2018

Copyright © 2009, 2010, 2012, 2016, 2018 IQVIA. All rights reserved. The contents of this document are confidential and proprietary to IQVIA Holdings Inc. and its subsidiaries. Unauthorized use, disclosure or reproduction is strictly prohibited.

Each protocol deviation is categorized into one of the following types, as reported in CTMS:

1. Informed Consent Criteria
2. Eligibility and Entry Criteria
3. Concomitant Medication Criteria
4. Laboratory Assessment Criteria
5. Study Procedures Criteria
6. Serious Adverse Event Criteria
7. Randomization Criteria
8. Visit Schedule Criteria
9. Investigation Product (IP) Compliance
10. Efficacy Criteria
11. Administrative Criteria
12. Source Document Criteria
13. Regulatory or Ethics Approvals Criteria
14. Other Criteria

Assignment to each analysis set, therefore whether a patient is included/excluded in each analysis set (excluding the PK analysis set, as this set will be defined later in a separate authorization with input, as required, from the PK scientist) will be recorded in an EXCEL sheet by the IQVIA Biostatistician, with the reason for exclusion from each population indicated. The EXCEL sheet should then be authorized by means of a customer authorization form (CAF) and prior to the Database Lock of the study.

10. DEMOGRAPHIC AND OTHER SCREENING CHARACTERISTICS

Demographic data and other screening characteristics (including screening disease characteristics) will be presented for each unique set, as described in Section 5. No statistical testing will be carried out for demographic or other screening characteristics. The following demographic and other screening characteristics will be reported for Part B:

- Age (years)
- Sex
- Childbearing potential

Document: Z:\RPL554\AZA40375\Biostatistics\Documentation\SAP\Verona RPL554-DP-201 SAP v2.0 – Part B

Author: [name] / [name]

Version Number: 2.0

Version Date: [08JUL2019]

Template No.: CS_TP_BS016 Revision 5

Reference: CS_WI_BS005

Effective Date: 01Apr2018

Copyright © 2009, 2010, 2012, 2016, 2018 IQVIA. All rights reserved. The contents of this document are confidential and proprietary to IQVIA Holdings Inc. and its subsidiaries. Unauthorized use, disclosure or reproduction is strictly prohibited.

- Race
- Ethnicity
- Height (inches)
- Weight (pounds)
- BMI (kg/m^2)
- Pre (prior to dosing at screening)/post (post dosing at screening) bronchodilator FEV₁ (both in liters and in percentage of predicted normal)
- Post-bronchodilator FEV₁/FVC
- Reversibility test (mL and %)
- Reversibility assessment performed with four puffs of Albuterol
- Met requirements of reversibility test

10.1. DERIVATIONS

Demographic and other screening characteristics recorded on the eCRF will be used as is on the eCRF, without any derivations or adjustments.

11. SURGICAL, MEDICAL AND CHRONIC OBSTRUCTIVE PULMONARY DISEASE/SMOKING HISTORY

Surgical and Medical History information will be presented in listings, for the RND analysis set.

- Surgical History will be coded by Medical Dictionary for Regulatory Activities (MedDRA) dictionary using the version specified in the data management plan.
 - Surgical History conditions are defined as those conditions which stop prior to or at Screening.
 - Data captured on the Surgical Procedure History page of the eCRF will be presented by SOC (System Organ Class) and PT (Preferred Term).
- Medical History will be coded by MedDRA dictionary using the version specified in the data management plan.
 - Medical History conditions are defined as those conditions which stop prior to or at Screening.
 - Data captured on the Medical History page of the eCRF will be presented by SOC and PT.

Document: Z:\RPL554\AZA40375\Biostatistics\Documentation\SAP\Verona RPL554-DP-201 SAP v2.0 – Part B

Author: [name] / [name]

Version Number: 2.0

Version Date: [08JUL2019]

Template No.: CS_TP_BS016 Revision 5

Reference: CS_WI_BS005

Effective Date: 01Apr2018

Copyright © 2009, 2010, 2012, 2016, 2018 IQVIA. All rights reserved. The contents of this document are confidential and proprietary to IQVIA Holdings Inc. and its subsidiaries. Unauthorized use, disclosure or reproduction is strictly prohibited.

- COPD/Smoking History data captured on the COPD and Smoking History page of the eCRF will be presented for each unique set, as described in Section 5.
 - COPD history (Duration of COPD (years) [calculated relative to date of first diagnosis {Randomization date, as recorded in Part A – first COPD diagnosis date}/365.25], date of most recent exacerbation, known to have chronic bronchitis/emphysema).
 - Smoking history (current or former smoker, number of packs per day, number of years smoking and number of pack-years [calculated as number of packs per day x number of years smoking])

12. MEDICATIONS

Medications will be coded using the World Health Organization – Drug Dictionary (WHO-DD) version specified in the data management plan and will be presented in a listing by Anatomical Therapeutic Chemical (ATC) (the 1st level of the ATC code) and PT for the RND analysis set. Certain medications (or a special grouping of medications) will be classified in a list during the study and signed-off prior to lock by a medical advisor. As this list, may change prior to sign-off they will not be defined in this section of the SAP. Potential medications include, but are not limited to, inhaled corticosteroids (ICS), LAMAs (long-acting muscarinic antagonists), LABAs (long-acting beta2-agonists) etc.

See [Appendix 2](#) for handling of partial dates for medications. In the case where it is not possible to define a medication as prior or concomitant, the medication will be classified by the worst case; i.e. concomitant.

- ‘Prior’ medications are medications which started and stopped in the time between Part A and Part B (prior to the study medication at TP1, Day 1) and have Started prior to start of study medication? = “Yes” on the Concomitant medications eCRF page.
- ‘Concomitant’ medications are medications which:
 - Had an onset date on or after the start of study medication for Part B (TP1, Day 1).
 - AND ended on or after the date of medication or were ongoing at the end of Part B.
 - A patient can report more than 1 concomitant medication with the same PT.

Prior and concomitant medications will be presented in a listing only, by treatment sequence. For concomitant medications, the treatment period when the medication was taken will also be reported in the listing.

Document: Z:\RPL554\AZA40375\Biostatistics\Documentation\SAP\Verona RPL554-DP-201 SAP v2.0 – Part B

Author: [name] / [name]

Version Number: 2.0

Version Date: [08JUL2019]

Template No.: CS_TP_BS016 Revision 5

Reference: CS_WI_BS005

Effective Date: 01Apr2018

Copyright © 2009, 2010, 2012, 2016, 2018 IQVIA. All rights reserved. The contents of this document are confidential and proprietary to IQVIA Holdings Inc. and its subsidiaries. Unauthorized use, disclosure or reproduction is strictly prohibited.

- Rescue medications will be recorded on the Rescue Medication Canister Collection/Rescue Medication Canister Dispensed/Rescue Medication Canister Weight pages of the eCRF. These are short acting bronchodilators and will be sourced by the study center and dispensed as needed during the Screening, treatment and washout periods. Rescue medication used during the study will be documented on the eCRF pages. Protocol procedures must continue even if rescue medication has been taken. Albuterol is to be used for primary rescue use, but others are also permitted (e.g. ipratropium). Rescue medications must be withheld for at least 8 hours prior to spirometry (per below), and this is to be confirmed in the eCRF at the start of each treatment period. If this withhold is not met, the patient should be rescheduled for a repeat visit within permitted windows.

Rescue medications used during study visits (by recording the time it was dispensed and collected) and the amount taken by treatment period (by recording the weight of the canister dispensed at the end of Day 1 and start of Day 7 per period), will be described in [Section 15.2.1.5](#).

When a rescue medication is used less than 8 hours prior to study medication a sensitivity analysis will be carried out for the analysis detailed in [Section 15.2.1.2](#) removed patients who took rescue medication. This will only be carried out if at least 1 patient has taken rescue medication less than 8-hours prior to study medications.

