3.2 Discussion of Study Design, including the Choice of Control Groups

Part A is designed as a single dose, parallel group study to evaluate the safety and terminal PK profile of a range of doses of RPL554 in a new DPI formulation compared to placebo. The safety and bronchodilatory response following a single dose will also be assessed.

In Part A, five dose levels ranging from 150 µg up to 6000 µg have been selected to evaluate the safety, PK and efficacy/pharmacodynamic characteristics of this formulation over a dose range covering a 40-fold increase in doses. A total of approximately 36 COPD patients aged 40 to 80 years (inclusive) will be randomized. Patients in Part A will be randomly assigned to receive either RPL554 or placebo via DPI. Following an analysis of the safety, PK and efficacy/pharmacodynamics, four doses will be selected for Part B. Study medication administered via DPI will be double blind, except for the 6000 µg treatment arm in Part A which

will be single blind due to the number of capsules required, in order to minimize any potential bias in the overall assessment of treatment effect and safety.

Part B is designed as a crossover study to assess the steady state efficacy/pharmacodynamic effect of four dose levels of RPL554 administered by DPI after a week of twice daily dosing, and to compare that effect with placebo DPI. Steady state PK and safety will also be assessed. One week of treatment was selected to evaluate efficacy/pharmacodynamics, PK and safety at steady state, as clinical data to date has shown that steady state PK is achieved after approximately 3 days of twice-daily dosing with the nebulized formulation.

In Part B, all patients from Part A will undergo five treatment periods in a double-blind randomized, crossover design; therefore, each patient will act as his or her own control. This design makes it possible to obtain unbiased inferences about differences between treatments, based on intra-patient differences.

The washout period between the treatment periods has been selected based upon the available PK of RPL554 in healthy volunteers, and patients with asthma or COPD. Five half-lives is considered as the time for elimination of RPL554 from the body. In this study, a washout period of 7 to 10 days from the last dose of study medication has been deemed adequate to ensure there was no overlap between the PK profiles of treatments with RPL554 in consecutive treatment periods.

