9.3.2.2 Secondary Endpoints

- Safety and tolerability:
 - Continuous monitoring of adverse events
 - Laboratory safety tests (hematology, blood chemistry and urinalysis)
 - 12-lead ECG (including QTcF and heart rate), supine vital signs (blood pressure and pulse rate)
- Change from baseline in (morning) trough FEV₁ measured prior to morning dosing on Day 7
- Change from baseline in peak FEV₁ measured after first dose
- Change from baseline in average FEV₁ AUC_{0-4h} measured after morning dosing on Day 7
- Change from baseline in average FEV₁ AUC_{0-12h} measured after first dose and after morning dosing on Day 7
- Determination of onset of action (>10% increase in FEV₁ from pre- to post- first dose, censored at 120 minutes) after first dose
- RPL554 steady state pharmacokinetics (AUC_{0-12h}, C_{max}, t_{max}, accumulation ratio) after dose 13 on Day 7
- Change from baseline in peak pulse after first dose on Day 1 and after morning dosing on Day 7
- Change from baseline in average FEV₁ AUC_{0-4h} and average FEV₁ AUC_{0-12h} on Day 1
- Change from baseline in rescue medication use

9.3.2.3 *Exploratory Endpoint*

- Evaluation of dose response of RPL554 on peak and average FEV₁ AUC_{0-12h} after morning dose on Day 7, and morning trough FEV₁ prior to the last dose on Day 7
- Change from baseline in Likert dyspnea scale measured after single dose and after morning dose on Day 7

9.4 *Statistical Methods*

In general, unless stated otherwise, continuous variables will be summarized using descriptive statistics (number of patients, mean, standard deviation, median, minimum and maximum values) and for categorical (nominal) variables, the number and percentage of patients will be used.

All hypothesis testing will be done using two-sided alternative hypotheses. P-values less than 5% will be considered statistically significant.

9.4.1 *Patient Disposition*

The number of patients enrolled, randomized, completed or withdrawn (with reason for withdrawal) will be summarized.

9.4.2 *Protocol Deviations*

All protocol deviations collected will be divided into critical, major or minor categories. Prior to database lock protocol deviations will be reviewed and consequences for inclusion of patients in various analysis population sets determined and documented.

9.4.3 *Demographics and Other Baseline Characteristics*

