9.5 Determination of Sample Size

The sample size is determined for Part B. This is a complete block crossover study. Assuming a residual CV of 6% for peak FEV₁, 30 patients will give an 80% power to detect a pairwise difference in peak FEV₁ of 4.6%. Assuming a mean baseline FEV₁ of 1.5 L this will correspond to a difference of about 70 mL. To account for withdrawals, 36 patients will be randomized to Part A.

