5. ANALYSIS SETS

Agreement and authorization of patients included/excluded from each analysis set will be conducted prior to the unblinding of the study for Part B.

In the case of dosing errors leading to duplication of treatment period or that treatment during period is undetermined, the period data for a patient could be excluded from the analysis. These will be agreed and documented prior to unblinding.

Document: Z:\RPL554\AZA40375\Biostatistics\Documentation\SAP\Verona RPL554-DP-201 SAP v2.0 – Part B

Author: [name] / [name]

Version Number: 2.0

Version Date: [08JUL2019]

Template No.: CS_TP_BS016 Revision 5

Reference: CS_WI_BS005

Effective Date: 01Apr2018

Copyright © 2009, 2010, 2012, 2016, 2018 IQVIA. All rights reserved. The contents of this document are confidential and proprietary to IQVIA Holdings Inc. and its subsidiaries. Unauthorized use, disclosure or reproduction is strictly prohibited.

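### The Part B rescue sensitivity analysis of Day 1 FEV1 removes patients, although the affected unit is one treatment period

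*SAP*

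**What the plan says.** SAP Part B Section 12 (Medications) sets the trigger as rescue use less than 8 hours before study medication, with at least one such patient. It names the analysis to be repeated, Section 15.2.1.2, and describes the repeat as run with "removed patients who took rescue medication". Section 15.2.1.2 covers secondary variables 4 to 6: Day 1 peak FEV1, average FEV1 over 0-4 h and average FEV1 over 0-12 h.

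Other provisions bear on the choice of unit:

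- **Withhold.** Section 12 has it confirmed in the eCRF at the start of every treatment period. Protocol 5.8.1 applies it before pre-dose spirometry on both Day 1 and Day 7.
- **Baseline.** SAP Part B 6.2 takes baseline afresh on Day 1 of each period.
- **Washout.** Periods are 7 to 10 days apart (SAP Part B 3.1).
- **Model.** Section 15.2.3.1 fits one mixed model over all periods with patient as a random effect.
- **Full analysis set.** Section 5.4 requires usable data from only two periods.
- **Dosing errors.** Section 5 says that "the period data for a patient could be excluded from the analysis".
- **Design rationale.** Protocol 3.2 says that "each patient will act as his or her own control".

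**The concern.** The trigger is an event at one dosing visit, but the unit removed is the patient. A short-acting bronchodilator taken before one Day 1 visit alters that visit's baseline and post-dose FEV1. It does not alter FEV1 measured in other periods, each of which has its own baseline after a washout. Removing the patient therefore also removes uncontaminated records, and it restricts the check to patients who did not use rescue before dosing.

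A sensitivity analysis is easiest to interpret when it differs from the main analysis only in the doubtful data. Here a shifted estimate or a wider interval could also come from the smaller sample or the narrower population.

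The sentence leaves two further matters open. It does not say whether the patients removed are only those inside the 8-hour limit or anyone who used rescue. Nor does it tie the trigger to the Day 1 dose, so a missed Day 7 withhold could remove a patient's Day 1 records, none of which that event touched.

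**Working it through.** **Inputs from the documents.** Protocol 9.5 takes the residual CV as 6% and states that "30 patients will give an 80% power to detect a pairwise difference in peak FEV₁ of 4.6" per cent. On the direction of tests, Protocol 9.4 says "All hypothesis testing will be done using two-sided alternative hypotheses"; on the level, the same section says "P-values less than 5% will be considered statistically significant". The ten sequences are in SAP Part B Appendix 1.

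**Inputs assumed.** The documents do not give the number of patients with rescue inside 8 hours, or the number of affected periods per patient. I take 1, 3 or 6 of 30 patients, with one or two affected periods each. Day 1 peak FEV1 is taken to have the 6% CV planned for peak FEV1.

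**Step 1: reproduce the plan's figure.**

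- Log-scale SD = sqrt(ln(1 + 0.06²)) = 0.0599
- SE of a pairwise contrast = SD × sqrt(2/30) = 0.01548
- Difference = ln(1.046) = 0.0450, so difference/SE is about 2.9
- Noncentral t, two-sided 5%, 29 df: power 0.802 and detectable difference 4.59%

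The stated 80% reproduces. With the residual degrees of freedom of the crossover model, 150 − 30 patients − 4 periods − 4 treatments − 1 covariate = 111, power is 0.821. That is the reference below.

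**Step 2: share of removed records that are clean.** A removed patient loses 5 records. With one affected period, 4/5 = 80% are clean. With two, 3/5 = 60%. With three, 2/5 = 40%. Most of the removed data are therefore clean only when one or two periods are affected.

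**Step 3: precision under each rule.** The SE of 3000 µg minus placebo comes from least squares with patient and period effects, with three patients on each of the ten sequences. Affected patients and periods are drawn at random, 200 draws per scenario. Patient effects are fixed, and the baseline covariate is allowed for only through 1 df. Each cell shows patient-level / period-level deletion, with one affected period per affected patient.

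| Patients affected | Records left | SE | SE relative to full data | Power for 4.6% |
|---|---|---|---|---|
| 0 | 150 | 0.01548 | 1 | 0.821 |
| 1 | 145 / 149 | 0.01575 / 0.01555 | 1.018 / 1.005 | 0.808 / 0.818 |
| 3 | 135 / 147 | 0.01635 / 0.01569 | 1.056 / 1.014 | 0.778 / 0.811 |
| 6 | 120 / 144 | 0.01738 / 0.01589 | 1.123 / 1.027 | 0.725 / 0.800 |

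A hand check of the last row: sqrt(30/24) = 1.118, close to 1.123. The small excess is the imbalance left when whole sequences lose patients.

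With two affected periods per patient the gap narrows: 0.808 / 0.814 for 1 patient, 0.778 / 0.801 for 3, and 0.726 / 0.777 for 6.

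Power is used here only as a readable scale for precision. The Day 1 variables are secondary and tested nominally (SAP Part B 7.4).

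**The case against.** **The wording may not mean whole patients.** The sentence is ungrammatical and does not say that all periods go. SAP Part B 5.3 counts a patient once per treatment received, and Protocol 9.2 lets the pre-lock meeting exclude specific data from a patient. This shows that the intent may have been narrower. But 5.3 is a counting rule for the safety set and 9.2 is general discretion. Neither turns a stated removal of patients into removal of periods.

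**The dosing-error precedent is only permissive.** Section 5 says that period data could be excluded, by agreement before unblinding. That is right. It shows that the SAP contemplates the period as a unit, not that it mandates it.

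**Few patients should be affected.** Protocol 5.8.1 and 6.4 and SAP Part B 12 call for rescheduling when the withhold is missed, and Protocol 9.4.8 makes the rescheduled visit the valid one. This stands. A reader might extrapolate to heavy losses: with 9 or 12 of 30 patients affected, the same calculation gives power of 0.663 against 0.788 and 0.592 against 0.778. No passage supports such frequencies. Nor can independence between periods be assumed: if rescue users are the more symptomatic patients, their events will cluster, and the clean share of what is removed falls.

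**The check would still be informative.** Agreement with the full-set result would be reassuring, and the remaining patients still give within-patient contrasts. This also stands. A reader might infer that the rule biases the dose comparisons or makes the check worthless. The Day 1 pre-dose event precedes that period's treatment, and the documents contain nothing with which to size a bias.

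**Other periods are not wholly untouched.** A Period 1 event also affects the reference for the ±20% pre-dose check in later periods (Protocol 3.2). That is true of the scheduling check, not of the later FEV1 values.

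**Conclusion.** The point holds, at minor severity. As written, the rule removes the wrong unit for a five-period crossover and leaves both its condition and its trigger open. The consequence is confined to a conditional sensitivity analysis of Day 1 secondary variables 4 to 6. A reader might take it to weaken the Day 7 primary result, but that analysis (SAP Part B 15.1) does not use this rule.

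The loss is mainly one of precision and breadth of population: about 1 power point with 1 affected patient, 3 points with 3, and 7 to 8 points with 6. These figures rest on 30 patients, a 6% CV carried over to Day 1, one affected period per affected patient and random placement of the events. The true number of affected patients is unknown and, given rescheduling, may be small.

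**What to change.** Replace the instruction in SAP Part B Section 12 with:

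> The sensitivity analysis excludes the Day 1 data of each treatment period in which rescue medication was taken less than 8 hours before the Day 1 morning dose of that period; the patient's other periods are retained.

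This settles the unit, limits the condition to use inside 8 hours, and keeps a Day 7 event from deleting Day 1 records. If the sponsor wants the stricter version, removal of the affected patients can stay as a second, clearly defined sensitivity analysis.

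The cost is one sentence and a filter by patient and period. The data set becomes slightly unbalanced, which the mixed model in Section 15.2.3.1 already allows.
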